7.0 STATISTICAL ANALYSES

Aim 1. Aim 1 of the proposed pilot study will evaluate the feasibility and acceptability of the proposed intervention. The feasibility of the study will be assessed by the following criteria displayed in Table 1.

Table 1. Feasibility and acceptability measures and benchmarks.

FEASIBILITY		
	Measure	Benchmark
Recruitment	Enrollment rate	7 participants/month
Intervention Adherence	Response rate to intervention messages Response rate to EMA prompts Fitbit use (% of days with > 8 hours wear time)	75% 75% 70%
Retention	Completion of follow-up assessments	90%
ACCEPTABILITY		
	Measure	Benchmark
Intervention satisfaction	Satisfaction questionnaire	75% of participants rate ≥ 4 on 5-point Likert scale

Aim 2.

Hypothesis 2a: *Participants will have greater daily step counts on days receiving an affective framing message compared to non-message days.*

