A repeated-measures mixed effects model will be used as described in Klasnja et al. (2015) with participant and time as random effects and other effects as fixed. Daily step count will be the dependent variable while main effects of affective framing intervention (message/no message) and linear time effects will be within-subjects factors, and an intervention by time interaction term will be included. We also will consider more complex effects of time (e.g., quadratic effects). We will include scores of the Physical Activity Intention, Physical Activity Self-Efficacy, and Affect as time-varying covariates. As described in Klasnja, et al. (2015) we will include the scores for the day prior to the intervention so the covariates will not be affected by the intervention. We will also classify each day as a cancer treatment day (i.e. day on which chemotherapy or radiation therapy is received) or not and presence/absence of cancer treatment will also be a time-varying covariate. A time lag is not needed for this covariate as the timing of cancer treatment will not be influenced by the intervention. Presence/absence of an implementation planning message on each day will also be included as a time-varying covariate and an affective framing by planning message interaction will be included to assess synergistic effects of the two messages. The baseline measurement of theoretical moderators of physical activity behavior change (Physical Activity Stage of Change, Physical Activity Self-Efficacy, Multidimensional Outcome Expectations for Exercise Scale) and psychosocial characteristics Functional Assessment of Cancer Therapy – General, Quick Inventory of Depressive Symptomatology – Self-Rated, Brief Fatigue Inventory) will be considered as covariates as will other baseline demographic and clinical variables determined to improve the fit of the final model.

Hypothesis 2b: *Participants will have greater daily step counts on days receiving the implementation planning message compared to non-message days.*

The same repeated-measures mixed effects model described for Hypothesis 2a will be used for this hypothesis. Only the interpretation of the results will be different as the presence/absence of the implementation message will be the main effect and the affective framing intervention will be considered the covariate.

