Hypothesis 2c: Participants randomized to receive feedback prompts reporting their highest daily step count will achieve greater step counts compared to participants that receive feedback prompts reporting their average daily step counts.

Participants will be randomized at baseline for the duration of the study because we expect that the intervention will have a cumulative effect over the course of the study. The hypothesis will be tested using a repeated-measures mixed effects model with participant and time as random effects and other effects as fixed. Daily step count will be the dependent variable. The intervention (highest vs average steps feedback) will be a between-subjects factor and time the within-subjects factor and an intervention by time interaction term will be included. We also will consider more complex effects of time (e.g., quadratic effects). The baseline characteristics described in Hypothesis 2a will be considered to improve the fit of the final model. We will also consider the inclusion of time-varying covariates if a clinically meaningful imbalance between groups is found.

Exploratory analyses

For Aim 2a and 2b we will also evaluate the moderating effects of time-varying factors measured through daily EMA (Physical Activity Intention, Physical Activity Self-Efficacy, and Affect). Our ultimate goal is to be able to evaluate these factors to inform decision rules in the ultimate adaptable intervention. The proposed sample size limits the power to detect time-varying moderators of intervention effects and formal analysis of moderating effects will only be conducted in the subsequent clinical trial. These analyses will use a repeated-measures mixed effects model as described above for Hypotheses 2a and 2b, and the moderating effect will be represented by a 3-way interaction of intervention, covariate, and time.

Power calculations

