The study design for Aims 2a and 2b will require subjects to be randomized each day to receive the intervention or not. Each day there will be a 50% probability of receiving the intervention (1:1 randomization schedule) so that the average subject will receive the intervention on 28 of the 56 study days. The sample size for Hypotheses 2a and 2b of 50 is based on the sample sizes in the table below which assume 80% power with an alpha=0.05. We also assume that the effect size (standardized difference between treatment groups, similar to Cohen's d) is constant during the 56-day study period. Note that for Cohen's d an effect size of 0.2 or less is considered 'small' (Cohen, 1998) (small effect=0.2, medium effect=0.5, large effect=0.8), therefore, the proposed sample size of 50 will be able to detect effect sizes that are about half of a 'small' effect.

The power analysis for Hypothesis 2c is based on a repeated measures analysis of variance comparison of two groups with 56 repeated observations assuming a correlation between repeated measurements of 0.5, 80% power, and alpha=0.05. Given these assumptions, an effect size of 0.29 can be detected with the proposed sample size of 50. Based on Cohen's guidelines for an ANOVA f-test an effect size of 0.29 is slightly larger than a 'medium' effect (small effect=0.1, medium effect=0.25, large effect=0.4).

Table 1. Sample size calculations.

Hypotheses 2a and 2b		Hypothesis 2c	
Effect Size	Sample Size to Obtain 80% Power	Effect Size	Sample Size to Obtain 80% Power
0.200	17	0.290	50
0.109	50	0.265	60
0.099	60	0.245	70
0.091	70	0.203	100
0.076	100	0.100	402

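### The exploratory analysis labels the three-way interaction with time as the moderating effect, but that term measures only how moderation changes over the eight weeks

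*Combined protocol and SAP*

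**What the plan says.** All references are to the combined protocol and SAP, Section 7.0.

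Under Exploratory analyses, for the two message components, the plan states that "we will also evaluate the moderating effects of time-varying factors measured through daily EMA", namely intention, self-efficacy and affect. The purpose is given as "Our ultimate goal is to be able to evaluate these factors to inform decision rules in the ultimate adaptable intervention". The model is to be the same mixed model as for the two message hypotheses. For the quantity of interest the plan then specifies: "the moderating effect will be represented by a 3-way interaction of intervention, covariate, and time".

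The plan limits the status of this work. It concedes that the sample size restricts power for time-varying moderators and says that "formal analysis of moderating effects will only be conducted in the subsequent clinical trial".

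The base model, under Hypothesis 2a, has the message and linear time as "within-subjects factors, and an intervention by time interaction term will be included". The EMA scores enter as covariates, taken from the day before. Quadratic time is left as an option. Neither place names an intervention × EMA-score term, lists the lower-order terms that go with the three-way interaction, or says how time is coded.

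**The concern.** A moderator of a message effect changes the size of the difference between message and non-message days. If a message works better on days with high intention than on days with low intention, that shows in intervention × intention. A three-way term that adds time asks a different question: whether this dependence strengthens or weakens over the study.

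The Hypothesis 2a model has the matching structure one level down. The main effect of the message carries the message effect, and intervention × time, listed separately, carries its change. The moderator sentence names only the counterpart of the second term.

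At stake is the estimate that is supposed to inform the decision rules. Under the hierarchical model, a useful and stable moderator would not show in the coefficient labelled as moderation. The caveat about power does not cover this, because a larger sample does not make the three-way term estimate stable moderation. If the sentence were carried into the subsequent trial, the greater size of that trial would not correct it.

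**Working it through.** **1. The plan's own figure.** For Hypotheses 2a and 2b the sample size table gives 50 participants for an effect of 0.109 at 80% power and alpha 0.05. Over 56 days with message probability 0.5, the noncentrality is λ = N × 56 × 0.25 × d² = 50 × 14 × 0.109² = 8.317. A noncentral F with 1 and N − 1 degrees of freedom gives power 0.807 at N = 50 and 0.799 at N = 49. The table's 50 is reproduced. The plan gives no figure for any moderation term.

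**2. What the named coefficient is.** Let A be the message, X the EMA score and t time. With all lower-order terms, the message effect is

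b_A + b_At·t + b_AX·X + b_AXt·X·t.

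Moderation at time t is b_AX + b_AXt·t, so b_AXt is the change in moderation per unit of time. If moderation is stable, b_AXt = 0 whatever the size of b_AX, and a test of b_AXt rejects at alpha. This step needs no assumed effect size.

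**3. Size, by closed form.** Assumptions not in the documents: score variance 1, within-person residual SD 1, moderation m in SD of daily steps per SD of score, constant over 56 days, two-sided 0.05, time centred.

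- Information on b_AX = 50 × 56 × 0.25 × 1 = 700, so SE = 1/√700 = 0.0378 and the 95% half-width is 1.96 × 0.0378 = 0.074.
- At m = 0.109: 0.109/0.0378 = 2.88; power = Φ(2.88 − 1.96) = 82%.
- With 75% of EMAs answered (the Table 1 benchmark for "Response rate to EMA prompts"): information 525, SE 0.0436, half-width 0.086, power 70%.

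**4. Size, by simulation.** 3,000 datasets per setting (1,000 for N = 400), exactly 28 message days per person, main effect 0.109, half the score variance between persons, all lower-order terms, time centred:

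| Stable moderation m | Two-way, all EMAs | Two-way, 75% of EMAs | Three-way |
|---|---|---|---|
| 0.054 | 28% | 23% | 5–6% |
| 0.10 | 74% | 61% | 5–6% |
| 0.109 | 82% | 70% | 5–6% |
| 0.15 | 97% | 93% | 5–6% |

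The simulated half-widths are about 0.075 and 0.087. At m = 0.109 with N = 400, the three-way rate is still 5%. A linear mixed model with random intercept and time slope and score autocorrelation 0.4 (336 datasets) gave 83% for the two-way and 6% for the three-way. A separate simulation (2,000 datasets per setting, person-specific intercepts and slopes removed, score autocorrelation 0.4) gave three-way rates of 5.0%, 5.2%, 5.6% and 5.0% for m = 0, 0.109, 0.2 and 0.5.

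**5. What the three-way term does detect.** The variance of t over days 1 to 56 is (56² − 1)/12 = 261.25. The SE of the change in moderation from day 1 to day 56 is therefore 55/√(700 × 261.25) = 0.129. Simulated power for a change of 0.1, 0.2, 0.3 and 0.4 SD is 12%, 32%, 62% and 86%.

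**6. Dependence on what the plan leaves open** (m = 0.109, no drift).

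- *All terms, time coded 1–56.* The two-way coefficient then refers to day 0. Its SE is 0.0378 × √(1 + 28.5²/261.25) = 0.0766, and power falls to 30% (28% simulated).
- *Two-way term omitted, time uncentred (1–56).* The three-way term absorbs stable moderation: its expected value is 0.109 × 28.5/1073.5 = 0.00289 per day, or 0.16 SD over 55 days, where the true change is zero. It rejects about 70% of the time.
- *Two-way term omitted, time centred.* The three-way term rejects about 5–6% of the time.

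**The case against.** The strongest reply is that the sentence describes a model and not a test. The base model already contains intervention × time, so adding a moderator leads naturally to a three-way structure. A hierarchical fit gives b_AX in the same output, and nothing says that only the highest-order coefficient will be reported. The analysis is exploratory and promises no moderation test at a stated alpha, so rejection rates are an imperfect yardstick. The sizes are assumed: m = 0.109 means the message effect doubles at +1 SD of score and vanishes at −1 SD. At about half that size the two-way test has only 28% power, in line with the plan's caveat. The base model also follows a cited methods source that is not available here.

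Much of this stands as a limit on consequence, and the size figures are illustrative. It does not rescue the sentence. On the hierarchical reading the wrong coefficient is still the one labelled as moderation. On the non-hierarchical reading the answer depends on how time is coded, as step 6 shows. Nor does the text show that drift was the target: in the Exploratory analyses paragraph, time-varying describes the EMA factors and not the moderation.

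One technical objection bears on the remedy. If the optional quadratic time terms also enter the interactions, the centred two-way coefficient becomes moderation at the midpoint. Its variance rises by a factor of 2.25, and power at 0.109 falls to 47–49%. Taking the two-way estimate from a model without the three-way term avoids this and gives 79–80%.

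**Conclusion.** The concern holds: the plan attaches the name of the moderating effect to the wrong term. That conclusion is algebraic, rests only on the lower-order terms being fitted, and does not depend on the size of the moderation. The contrast in size (82% against 6% at 0.109 SD per SD, or 70% against 5–6% with 75% EMA response) rests on the assumed moderation, score variance and residual structure. Small moderation would stay imprecise even with the right term.

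The consequence is limited to the exploratory estimate intended for the decision rules. The tests of Hypotheses 2a, 2b and 2c, the sample size of 50, the Aim 1 benchmarks and the data to be collected are unaffected. It should be corrected before analysis, but it does not threaten the study's main conclusions.

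**What to change.** Replace the sentence on the three-way interaction with wording to this effect:

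- The moderation estimand for each EMA factor is the two-way intervention × EMA-score interaction. It is fitted with all its lower-order terms and with time centred, and reported as an estimate with a 95% confidence interval.
- The estimate is taken from the model without the three-way term, so that it does not depend on where time is centred or on whether quadratic time enters the interactions.
- The three-way term is then added, with all lower-order terms, as a secondary check for drift in moderation.
- The plan's existing principle stays: the score must be measured before the prompt whose effect it is meant to moderate.

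The cost is one or two sentences of SAP text. No new data are needed and the analysis remains exploratory.

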8.0 REPORTING AND MONITORING

8.1 Statement of Compliance

This trial will be conducted in compliance with the appropriate protocol, appropriate ICH guidelines (including current Good Clinical Practice [GCP]), the principles of the Declaration of Helsinki, and all other applicable regulatory requirements. The study team must obtain written approval of the study protocol, consent form, other supporting documents, and any advertising for participant recruitment from the UT Southwestern institutional review board (IRB) in order to participate in the study. Prior to study initiation, the protocol and the informed consent documents will be reviewed and approved by an appropriate UT Southwestern IRB. Any amendments to the protocol or consent materials must be approved before they are implemented. Annual progress reports and Serious Adverse Event (SAE) reports will be submitted to each IRB, according to its usual procedures.

8.2 Regulatory Files

The regulatory files should contain all required regulatory documents, study-specific documents, and all important communications. Regulatory files will be reviewed at each participating site for regulatory document compliance prior to study initiation, throughout the study, as well as at the study closure.

8.3 Informed Consent

Every study participant is required to sign a valid, IRB-approved current version of the study informed consent form prior to the initiation of any study related procedures.

Prior to signing the informed consent form, research staff who are knowledgeable about the study will explain the study to the potential participant and provide the participant with a copy of the consent to read. If the participant is interested in participating in the study, a researcher who is authorized to obtain informed consent will review each section of the informed consent form in detail, answer any of the participant's questions. The participant will consent by signing and dating the consent document. The person obtaining consent will also sign and date the consent document. Every study participant must be offered a copy of the signed consent form. The consent must be properly executed and complete to be valid. All persons obtaining consent must have completed appropriate training.

The informed consent form must be updated or revised whenever important new safety information is available, or whenever the protocol is amended in a way that may affect a participants' participation in the trial.

Study participation is voluntary and there are no benefits lost if an individual declines participation. Individuals who refuse to participate or who withdraw from the study will be treated without prejudice. Study sites will be responsible for maintaining signed consent forms as source documents for quality assurance review and regulatory compliance.

8.4 Study Documentation

Study documentation includes all case report forms, source documents, monitoring logs, Institutional Review Board correspondence and approved consent form and signed participant consent forms.

Source documents include all recordings of observations or notations of clinical activities and all reports and records necessary for the evaluation and reconstruction of the clinical research study. Whenever possible, the original recording of an observation should be retained as the source document; however, a photocopy is acceptable provided that it is a clear, legible, and exact duplication of the original document.

8.5 Records Retention and Requirements

All research records for all subjects will be stored by the investigator in a secure location to be accessed only by authorized research personnel. Study records will be stored in accordance with local IRB, State, and Federal Regulations but, in any case, will be kept for a minimum of 2 years following study completion.

8.6 Reporting to Sponsor

The principal investigator will submit any and all required reports accurately to the sponsor in a timely manner. Reports may include any significant changes possibly affecting the safe and accurate conduct of the trial or its outcomes. The principal investigator will also submit to the sponsor a detailed final report on the study at its conclusion.

8.7 Safety Monitoring

8.7.1 Data and Safety Monitoring

On a monthly basis, [name] will examine accumulating data to assure protection of participants' safety while the study's scientific goals are being met. These meetings will determine whether there is support for continuation of the trial, or evidence that study procedures should be changed, or if the trial should be halted, for reasons relating to the safety of the study participants, or inadequate trial performance (e.g., poor recruitment).

8.7.2 Protocol Violations Reporting and Management

A protocol departure is any departure from procedures and requirements outlined in the protocol. Protocol departures may occur on two levels, deviation versus violation. The difference between a protocol deviation and violation has to do with the seriousness of the event and the corrective action required. A protocol deviation is considered an action (or inaction) that by itself is not likely to affect the scientific soundness of the investigation or seriously affect the safety, rights, or welfare of a study participant. Protocol violations are departures that may compromise the participant safety, participant rights, inclusion/exclusion criteria or study data and could be cause for corrective actions if not rectified or prevented from re-occurrence. Protocol violations will be monitored for (1) significance, (2) frequency, and (3) impact on the study objectives, to ensure the integrity of the trial. The PI or designee will make the decision about whether a departure from the protocol will be designated as a protocol deviation or a protocol violation. All protocol violations and deviations will be reported to the IRB as required.

8.7.3 Subject Confidentiality/Privacy

Participant records will be held confidential by the use of study codes for identifying participants on CRFs, secure and separate storage of any documents that have participant identifiers, and secure computing procedures for entering and transferring electronic data.

All research information obtained on participants is confidential, and disclosure to any third parties without specific authorization is strictly prohibited. To maintain subject privacy, all study forms and reports will be identified by a coded study identification number only. No subject identifying information will be included in any presentations or publications resulting from the study.

Study records may be inspected by the sponsor and its authorized representatives, other government agencies such as the U.S. Department of Health and Human Services (DHHS) Office for Human Research Protections (OHRP), authorized Node Staff, or the local IRB for quality assurance purposes.

8.7.4 Adverse Events (AEs) and Serious Adverse Events (SAEs)

The Primary Investigator (PI) will review or seek consultation for each Serious Adverse Event (SAE) as needed. These reviews will include an assessment of the possible relatedness of the event to the study intervention or other study procedures. The PI will also provide advice for decisions to exclude, refer, or withdraw participants as required. The study staff will be trained to monitor for and report Adverse Events and Serious Adverse Events.

8.7.5 Reporting Adverse Events and Serious Adverse Events

Adverse Events

Adverse events severe in nature (grade 3) will be documented from the time consent is signed through the end of study participation.

For the purpose of this study, the following AEs will not require reporting in the participant's record and will not be captured:

- Grade 1 (mild) unrelated event.
- Grade 2 (moderate) unrelated event.

Serious Adverse Events

For the purpose of this study, all SAEs will be documented in the participant's record with the exception of the following:

- Admission to a hospital/surgery center for preplanned/elective surgeries (captured in the Visit Summary/Progress Note).
- Admission to a hospital for scheduled labor and delivery (captured in the Visit Checklist/Progress Note).

Local documentation and reporting guidelines should also be followed based on local IRB requirements.

